As sensitivity analysis, the change in a cortical composite SUVR from baseline to 3 years will also be analyzed based on a repeated measures ANCOVA model in which treatment, age stratification factor, MMSE stratification factor, region, baseline cerebrovascular disease burden as measured by MRI, APOE4 status (carrier vs. non-carrier), baseline amyloid status (positive/negative), visit (18 months, 3 years), and treatment-by-visit interaction will be included as fixed-effect factors and baseline value and baseline-by treatment as covariates, with a common unstructured covariance matrix among visits between treatment group. The adjusted mean changes at 3 years (Week 156) within each treatment, the difference in mean changes at 3 years (Week 156) between two treatments, its 95% confidence interval obtained from the above model will be presented. The analysis is based on likelihood method with an assumption of missing at random for missing data. A three month window will be applied to re-map any unscheduled visit assessments to a missing scheduled visit assessment.

In addition, to assess the sensitivity of the MAR assumption used in multiple imputation, analyses based on multiple imputations, such as those using a pattern mixture model approach,

may be performed, which assumes that missing values after death, HF hospitalizations, stroke were missing not at random (MNAR).

A shift table to summarize the proportion of patients' amyloid status change over time from baseline by treatment will be provided as well.

All analyses will be performed in patients in the Safety set who participate in the PET image substudy, including 'on-treatment' data only. On-treatment data refer to the SUVR values obtained while patients are on-study-medication (regardless of treatment interruption) or within six months after final study drug intake date.

[figure not shown]

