2.5.2 Statistical hypothesis, model, and method of analysis

The change from baseline in the GCCS of CogState test battery will be analyzed using a repeated measures analysis of covariance (ANCOVA) model in which treatment, age stratification factor, MMSE stratification factor, education level, APOE4 status (carrier vs. non-carrier), baseline cerebrovascular disease burden, visit (Weeks 26, 52, 78, 104, 130 and Week 156) and treatment-by-visit interaction are included as fixed-effect factors and baseline GCCS and visit-by-baseline GCCS interaction as covariates, with a common unstructured covariance matrix among visits between treatment groups. The adjusted mean changes at 3 years (Week 156) within each treatment, the difference in mean changes at 3 years (Week 156) between the two treatments, and its 95% confidence interval obtained from the above model will be presented. In addition, the treatment difference (LCZ696-valsartan) in mean changes from baseline to 3 years will also be expressed based on a standardized effect size (Cohen's d) with a 2-sided 95% confidence interval. The Cohen's d will be estimated by using the adjusted between-treatment mean difference, divided by the estimated pooled standard deviation. The estimated standard deviation for the mean difference is:

$$SD = \left(\frac{1}{n_1} + \frac{1}{n_2} \right)^{1/2} \hat{\sigma}$$

where n1 and n2 are the number of patients within each treatment group and $\hat{\sigma}$ is the pooled standard deviation of the within treatment group adjusted mean change. Cohen's d can be rewritten in terms of t value of the estimated between treatment group difference based on the adjusted mean changes from the model mentioned above:

$$t = \frac{\hat{\mu}_1 - \hat{\mu}_2}{SD} = \frac{\hat{\mu}_1 - \hat{\mu}_2}{\left(\frac{1}{n_1} + \frac{1}{n_2} \right)^{1/2} \hat{\sigma}}$$

$$\hat{d} = \frac{\hat{\mu}_1 - \hat{\mu}_2}{\hat{\sigma}} = \left(\frac{1}{n_1} + \frac{1}{n_2} \right)^{1/2} \times t$$

Confidence interval (CI) of Cohen's d is based on 95% CI of the noncentrality parameter of t value divided by the square root of the degrees of freedom from the estimated between treatment group adjusted mean change (Cumming and Finch 2001). The analysis is based on a direct likelihood method with an assumption of missing at random (MAR) for the missing data mechanism.

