The imputation model will include age stratification factor, MMSE stratification factor, region, baseline cerebrovascular disease burden, APOE4 status (carrier vs non-carrier), baseline amyloid status (positive/negative) and time (when the SUVr is assessed in days) as fixed effects with random intercept and slope (time) and a common unstructured covariance. This will be done separately within each treatment. Missing values will be imputed by the predicted values following from the fitted imputation model with random effects and random errors simulated from their respective distributions. SAS proc MCMC is used to impute missing values described above.

This imputation process will first create multiple imputations of missing SUVr at 3 years under a MAR assumption, resulting in multiple complete data sets after combining the imputed missing SUVr at 3 years values with the available SUVr at 3 years (so every patient with baseline SUVr in these multiple complete data sets will have an SUVr value at 3 years). An ANCOVA model using change from baseline to 3 years in SUVr as response variable, with treatment, age stratification factor, MMSE stratification factor, region, baseline cerebrovascular disease burden, APOE4 status, baseline amyloid status as factors and baseline SUVr value and treatment-by-baseline SUVr interaction as covariates will be run on each of these multiple completed data sets. Overall results and inference, including adjusted mean change at 3 years within each treatment, the difference in mean change at 3 years between two treatments, its 95%

confidence interval, are obtained by applying Rubin's rules on the estimates obtained from the imputed/completed data sets.

If convergence issue arises, the imputation model will be modified by replacing the common unstructured covariance with a common compound symmetry covariance between treatment groups. If convergence issue remains after implementing the compound symmetry covariance matrix, the model will be simplified by removing baseline cerebrovascular disease burden as explanatory factory from the model.

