2.7.1.1 Supportive analysis

Both the actual SUVr values and change from baseline values will be descriptively summarized for each treatment group by each assessment visit over study period by providing summary statistics (n, mean, SD, median, Q1, Q3, min, max). Additionally, number and percentage of patients with positive PET scan will be reported for each treatment group by each assessment visit. Available SUVr data at 'end of treatment' and 'end of study' will be summarized separately as above.

To assess the sensitivity of the primary analysis method results to the imputation model, a sensitivity analysis will be performed on the change in a cortical composite SUVr from baseline to 3 years by incorporating information from other assessments still under the assumption of MAR. The change from baseline in SUVr will be analyzed based on a repeated measures ANCOVA model in which treatment, age stratification factor, MMSE stratification factor, region, baseline cerebrovascular disease burden, APOE4 status (carrier vs. non-carrier), baseline amyloid status (positive/negative), visit (18 months, 3 years), and treatment-by-visit interaction will be included as fixed-effect factors and baseline value and baseline-by-treatment as covariates, with a common unstructured covariance matrix among visits between treatment groups. The adjusted mean changes at 3 years (Week 156) within each treatment, the difference in mean changes at 3 years (Week 156) between two treatments, its 95% confidence interval obtained from the above model will be presented. The analysis is based on likelihood method with an assumption of missing at random for missing data.

To assess the sensitivity of the primary analysis methods results to the baseline amyloid status (positive/negative) based on quantitative (numerical) cutoff instead of qualitative (visual) assessment, a sensitivity analysis will be performed using the same ANCOVA model specified in [Section 2.7.1](#) but with the quantitative positive/negative assessment of the baseline brain amyloid status. A shift table to summarize the proportion of patients' amyloid status change over time from baseline i.e. patients transitioning from negative to positive based on quantitative assessment will also be provided by treatment group.

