2.11 Biomarkers

[figure not shown]
For plasma A β 1-40, the log-transformed ratio to baseline i.e. $\log(\text{post-dose value}/\text{baseline})$ will represent the change from baseline in logarithmic change for each subject at every post-dose time point. The change from baseline to a pre-defined time-point (Weeks 13, 52, 104 and 156) in logarithmic scale will be analyzed using a repeated measures ANCOVA model in which treatment, age stratification factor, MMSE stratification factor, education level, APOE4 status (carrier vs. non-carrier), visit (Weeks 13, 52, 104 and Week 156) and treatment-by-visit interaction are included as fixed-effect factors and baseline log-transformed plasma A β 1-40 and visit by baseline log-transformed plasma A β 1-40 interaction as covariates, with a common unstructured covariance matrix among visits between treatment groups. The adjusted mean changes within each treatment, the difference in mean changes between the two treatments, and its 95% confidence interval obtained from the above model will be presented for all the assessment visits. All the estimates will be back-transformed to natural scale for reporting.

[figure not shown]
Descriptive summaries of absolute values and change from baseline in A β 1-40 by treatment group and visit will be presented using summary statistics (n, mean, SD, median, minimum, maximum, Q1, Q3, geometric mean and Coefficient of Variation). Mean A β 1-40 levels will also be graphically presented by each visit over study period for each treatment group.

[figure not shown]
All of the above analyses will be performed for patients for whom the biomarker data is obtained in the PET imaging substudy with non-missing baseline including all data.

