3.2 Sample size calculation for the PET imaging substudy

Approximately 300 complete patients (in 1:1 allocation ratio to LCZ696 and valsartan) will provide at least 80% probability that the 2-sided 95% CI excludes a between-treatment absolute difference of 0.01 (corresponding to an incremental 33% increase in LCZ696 vs. valsartan) in change from baseline in SUVr over 3 years if there is no expected difference between two treatments. This calculation is based on the assumptions that the mean change over 3 years from baseline in SUVr is 0.03 in the control group, the common standard deviation is 0.03 (estimated from ADNI data, [Chen et al 2015](#)). It is noted that the ADNI data presented in Chen's paper are by patients' cognitive status (normal, MCI, dementia) and for changes over two years. The assumptions used here are guestimates from the 2 year data in normal cognitive and MCI subjects.

An absolute difference in SUV ratio of 0.01 was considered small as it represents a value that is lower than the rate of SUVr change that distinguishes between amyloid positive and negative patients (0.026 vs. 0.011).

Sample size calculation was performed using N-Query 7.0.

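### The SUVr repeated-measures sensitivity model has no visit-by-baseline term, so within each arm the baseline slope is held equal at 18 months and 3 years; the likely cost is small and adding the term is almost free

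*SAP*

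**What the plan says.** SAP 2.7.1.1 sets out a repeated-measures ANCOVA of SUVr change to test how far the primary result depends on the imputation model. Its visit terms are given as "visit (18 months, 3 years), and treatment-by-visit interaction will be included as fixed-effect factors", its baseline terms as "baseline value and baseline-by-treatment as covariates", and it is fitted "with a common unstructured covariance matrix among visits between treatment groups". Protocol 9.5.2 lists the same baseline terms: "baseline value and baseline-by treatment as covariates". Baseline amyloid status is also a factor, again without a visit interaction. Neither document explains the choice.

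Other models in the plan are built differently:
- The primary cognitive model (SAP 2.5.2) has "baseline GCCS and visit-by-baseline GCCS interaction as covariates". The domain and FAQ models (SAP 2.6.2) reuse it with their own baselines.
- The plasma Aβ1-40 model (SAP 2.11) has "visit by baseline log-transformed plasma" as an interaction.
- The primary SUVr analysis (SAP 2.7.1) imputes with a random intercept and slope over time and then fits a 3-year ANCOVA: "baseline SUVr value and treatment-by-baseline SUVr interaction as covariates will be run on each of these multiple completed data sets". With one time point, there is no visit over which a slope could be held constant.

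**The concern.** Baseline-by-treatment lets the baseline slope differ between arms, but within an arm one coefficient serves both visits. The unstructured covariance does not relax this, because the restriction is on the mean. If patients with more amyloid at baseline accumulate it faster, their lead widens with time. The true slope is then steeper at 3 years than at 18 months, and a shared slope fits neither visit.

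Two things could follow at 3 years. Part of the baseline effect stays in the residual and widens the interval. And if the arms lose high-SUVr patients at different rates, the incomplete adjustment leaves a bias in the treatment difference.

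There is also a question of purpose. The model exists to check the imputation model, yet it adds a restriction that the primary route lacks. If the two results differed, the reader could not tell which feature was responsible.

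**Working it through.** **The plan's own PET figure.** SAP 3.2 asks for at least 80% probability that "the 2-sided 95% CI excludes a between-treatment absolute difference of 0.01", with SD 0.03 and 300 complete patients.
- Needed per arm: 2 × (1.960 + 0.842)² × 0.03² / 0.01² ≈ 141.3, so 142 (284 in total).
- At 150 per arm: 0.01 / (0.03 × √(2/150)) = 2.887, and Φ(2.887 − 1.960) = 82.3%.
- Randomized: 300 / 0.7 = 429; the SAP says 430.

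These reproduce. The point below does not touch them.

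**What the constraint does.** Let the true baseline slopes be β18 and β36, and let b be the shared fitted slope. At 3 years the residual variance gains (β36 − b)² × Var(baseline). Any bias in the treatment difference is roughly proportional to (β36 − b) times the difference between arms in mean baseline among patients still measured at 3 years. Both vanish if β18 = β36. The bias also vanishes if leaving depends on baseline equally in both arms.

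**Simulation A.** From the documents: 430 patients, 1:1, two visits, unstructured covariance, 30% missing at 3 years, SD of 3-year change 0.03. True difference 0; 1,000 runs per case. Assumed, because the documents give no values: SD of 18-month change 0.02; residual correlation 0.5; correlation of baseline with 3-year change 0.2, 0.4 or 0.6; log-odds of leaving ±0.7 per baseline SD where leaving depends on baseline. Monte Carlo error of a bias is about 0.0032 / √1000 = 0.0001.

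| Correlation | 18-month slope ÷ 3-year slope | High-SUVr patients leave more | SE as written | SE with term | Bias as written | Bias with term |
|---|---|---|---|---|---|---|
| 0.2 | 1 | no | 0.00326 | 0.00326 | 0.0001 | 0.0001 |
| 0.2 | 0.5 | no | 0.00328 | 0.00326 | 0.0001 | 0.0001 |
| 0.2 | 0.5 | both arms equally | 0.00331 | 0.00330 | 0.0000 | 0.0000 |
| 0.2 | 0.5 | LCZ696 only | 0.00329 | 0.00329 | −0.0005 | 0.0001 |
| 0.2 | 0.5 | LCZ696; reverse on valsartan | 0.00331 | 0.00335 | −0.0011 | 0.0001 |
| 0.4 | 0.5 | no | 0.00312 | 0.00305 | 0.0001 | 0.0001 |
| 0.4 | 0.5 | LCZ696 only | 0.00313 | 0.00308 | −0.0011 | 0.0001 |
| 0.6 | 0.5 | no | 0.00282 | 0.00266 | 0.0001 | 0.0001 |
| 0.6 | 0.5 | LCZ696 only | 0.00283 | 0.00269 | −0.0017 | 0.0001 |

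With leaving unrelated to baseline, the SE cost is 0.6%, 2% and 6% at correlations 0.2, 0.4 and 0.6. At correlation 0.2 with leaving on LCZ696 only, coverage is 94.0% as written and 94.5% with the term.

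**Which row is realistic.** The only figure in the documents is a change of 0.026 in amyloid-positive and 0.011 in amyloid-negative patients (SAP 3.2), with no time unit. Read on the 3-year scale, the correlation of status with change is 0.015 × √(p(1 − p)) / 0.03, where p is the share positive:
- p = 30%: 0.015 × 0.458 / 0.03 = 0.23
- p = 10%: 0.015 × 0.300 / 0.03 = 0.15
- p = 5%: 0.015 × 0.218 / 0.03 = 0.11

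Read per year, the contrast and these correlations triple (0.69, 0.45, 0.33). But the mean 3-year change at p = 10% would then be 3 × (0.1 × 0.026 + 0.9 × 0.011) = 0.0375, and at p = 30% it would be 0.0465, against the 0.03 that the plan assumes.

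The SAP document history (June 2022) says that amyloid-positive patients were so few that imputation within that stratum could not be done. This points to a small p.

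**Simulation B.** 215 per arm, with the amyloid-status factor in the model as planned; measurement-error SD 0.017, slope SD 0.006 per year, and the baseline distribution assumed; 3-year loss among positives 45% on LCZ696 and 30% on valsartan, and 30% among negatives; 800 runs per case.
- 3–5% positive: SE gain from the term 0.03–0.35%; bias −0.00004 to −0.0003, changing by at most 0.0001 when the term is added.
- 10% positive: SE gain 0.2–0.9%; bias −0.0001 to −0.0003.
- Loss pattern swapped between arms: the sign reverses (+0.0003).

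**The case against.** The best case for leaving the model alone is that nothing turns on it. It is one of several supportive analyses of a secondary endpoint. The primary SUVr analysis is free of the constraint, and baseline-by-treatment mirrors the ANCOVA in SAP 2.7.1. The part of the baseline slope that comes from regression to the mean is equal at both visits, so the fitted slope need not scale with time. The term is also not a full cure: amyloid status has no visit interaction either, and with 30% positive a bias of about −0.0003 remained after visit-by-baseline was added. All of this stands. It limits the point to a small improvement but does not justify the restriction.

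A reader might infer more than the documents support:
- **A larger effect.** With 30% positive and per-year rates, the SE falls from 0.00359 to 0.00346 (3.6%) when the term is added, and the bias as written is −0.0008, 8% of 0.01. That share does not fit the SAP's own account of very few positives, and those rates do not fit its assumed mean change.
- **A bias that favours LCZ696.** This needs more high-SUVr patients to leave LCZ696, and no passage says so. Protocol 9.4.4 and SAP 2.5.5 contemplate lower mortality on LCZ696, which could mean more loss on valsartan and the opposite sign. Investigators are blinded to amyloid status and SUVr, which weakens any link between high SUVr and leaving.
- **A unique omission.** The exploratory models are redacted, so only the visible ones can be compared.

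**Conclusion.** The point holds as a minor one. The model as written fixes the baseline SUVr slope across visits within each arm, unlike the plan's other visible repeated-measures models and without a stated reason.

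The likely precision cost is under about 1% of the SE of the 3-year difference. It would be about 2% if baseline and 3-year change correlated at 0.4, and zero if the true slopes are equal. Bias in the treatment difference arises only if leaving depends on baseline SUVr differently by arm. It is then likely about 0.0005 or less (0.0005 / 0.01 = 5% of the difference to be excluded), in either direction. Larger values need stronger correlations, or opposite leaving patterns in the two arms.

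These sizes rest on assumed inputs, since the documents give no baseline SUVr SD and no baseline–change correlation, and on the assumption that the baseline effect grows with follow-up. The primary SUVr analysis and the PET sample size are not affected.

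**What to change.** In SAP 2.7.1.1, change the covariates of the repeated-measures SUVr model to *baseline value, baseline-by-treatment and visit-by-baseline*, in line with SAP 2.5.2 and 2.11. Align the matching sentence in protocol 9.5.2, or record the difference in SAP Section 4, which at present lists no changes to the protocol's analyses. The cost is one model term and one degree of freedom, with about 430 patients planned for the substudy; no new data are needed. In return, a disagreement with the primary result can no longer be put down to this constraint.

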Note that negative sign is included in the calculation for tasks where increasing values indicate worsening performance (i.e., Z_{DET} , Z_{IDT} , Z_{CPAL} , Z_{ONB} and Z_{GMLT}) so that for all standardized change scores negative values indicate a decline from baseline while positive scores indicate improvement from baseline.

These seven individual z-scores are then combined to generate the GCCS:

CogState GCCS = average of (Z_{DET} , Z_{IDT} , Z_{CPAL} , Z_{ONB} , Z_{ISLT} , $Z_{ISLT-DR}$, Z_{GMLT})

The composite score will be computed if at least five of the seven tests are completed and the five tests provide an assessment of the three cognitive domains as defined below being assessed. That is, a composite score requires that each cognitive domain be measured by at least one cognitive test.

In addition to the GCCS, composite scores for three main subdomains memory, attention and psychomotor function will also be generated by combining the standardized change from baseline scores for individual tests from the CCB using the following formulae:

- Composite score of memory tests = average of (Z_{CPAL}, Z_{ISLT}, Z_{ISLT-DR})
- Composite score of executive function tests = average of (Z_{ONB}, Z_{GMLT})
- Composite score of attention tests = average of (Z_{DET}, Z_{IDT})

Each composite score will be the average of the non-missing individual test z-scores.

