1. Multiple (e.g. 100) imputations of missing GCCS values under a MAR assumption are generated, resulting in multiple (100) complete data sets. This imputation is based on predicted GCCS values from the fitted repeated measures ANCOVA model for the GCCS values (at baseline, Weeks 26, 52, 78, 104, 130 and Week 156) with treatment, age group (<75, ≥75 years), baseline MMSE status (<28, ≥28), baseline cerebrovascular disease burden, visit and treatment-by-visit interaction as factors having fixed effects assuming a common unstructured covariance matrix among visits between treatment group. SAS proc MI FCS statement is used to impute missing values in the following sequence: factor variables in the increasing order of missing frequency, the GCCS at baseline, Weeks 26, 52, 78, 104, 130 and Week 156.
2. For each completed data set, the imputed GCCS values at a given visit for patients who died, or had a HF hospitalization or stroke since the preceding visit, a penalty factor would be applied to the imputed values to reflect that the MAR approach may have overestimated the missing values, e.g. by assuming the actual GCCS values could be a certain percentage (e.g. 5%) worse than MAR based imputations for discontinuations due to death, HF hospitalization and stroke. If the MAR-imputed GCCS value is positive, the final value will be 95% x the imputed value; if the MAR-imputed GCCS value is negative, the final value will be 105% x the imputed value.
3. The primary analysis model as described above will be fitted to the 100 completed data sets following the application of the penalty factor in step 2 which produces 100 sets of parameter estimates and associated covariance matrices.
4. These 100 sets of parameter estimates are then combined by using Rubin's rules to derive overall estimates and their confidence intervals. In a similar manner to the primary analysis, a standardized effect size estimate (Cohen's d) and 95% CI will also be reported using the pooled SD.

The analysis will be repeated for varying penalty factors in a range between 0 and 50%. It is performed using 'on-treatment' data in the SAF, as done in the primary analysis. Tipping point analyses will be performed separately to assess the sensitivity of the results to MAR assumptions under the following situations:

- for missing data due to censoring at the start of AD and cognitive impairment treatments, including on-treatment data only in the SAF

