In addition, to assess the sensitivity of the analysis results to the MAR assumption used in the multiple imputation for primary analysis method, a tipping point analysis will be performed on the change from baseline in SUVr which assumes that missing values after death, HF hospitalization and stroke are missing not at random (MNAR). This analysis will follow the same procedure as described in [section 2.5.5](#) for the primary endpoint, with the exception that the imputations under MAR are obtained from a regression based imputation as described in the primary analysis method of this endpoint ([Section 2.7.1](#)). The analysis will be repeated for varying penalty factors in a range between 1 and 1.6.

[figure not shown]
If convergence issue arises in any of above described supportive analyses, the handling approach described in [Section 2.7.1](#) will be used to address the convergence issue.

[figure not shown]
Furthermore, to assess the sensitivity of the analysis results to the randomization stratification that is done incorrectly due to transcription error or inconsistent site and central reviewer readings, analysis described in [Section 2.7.1](#) will be repeated using the final data entered in the clinical database, instead of the stratification factors based on IVR system.

[figure not shown]
To address missing assessments due to COVID-19 pandemic, the analysis mentioned in [Section 2.7.1](#) will be repeated using PET substudy set with a wider assessment window extending from 6 months to 9 months for assessments that are scheduled to take place starting Mar 1, 2020 and onwards. This also applies to the data excluded from analysis if assessment is done more than 9 months after last study drug intake instead of 6 months.

[figure not shown]
All analyses will be performed in patients in the Safety set who participate in the PET image substudy and with non-missing baseline, including ‘on-treatment’ data only. On-treatment data refer to the SUVr values obtained while patients are on-study-medication (regardless of treatment interruption), or within defined window in each supportive analysis (six months or nine months) after the final study drug intake date.

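### The SUVr tipping-point analysis borrows a penalty rule that runs the wrong way for amyloid and does not fit its own 1 to 1.6 range, so it does not reliably stress the result

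*SAP*

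**What the plan says.** SAP 2.7.1.1 states that "a tipping point analysis will be performed on the change from baseline in SUVr", treating values missing after death, HF hospitalisation or stroke as missing not at random (MNAR). The method is taken over from SAP 2.5.5 (the sentence opens "This analysis will follow the same procedure as described in"), and one departure is allowed, which concerns only where the imputations come from: "with the exception that the imputations under MAR are obtained from a regression based imputation". No other exception is named. The range follows: "The analysis will be repeated for varying penalty factors in a range between 1 and 1.6".

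The imported procedure is step 2 of the tipping-point analysis in SAP 2.5.5, written for GCCS. Its worked example is a 5% penalty, and for values above zero it reads: "If the MAR-imputed GCCS value is positive, the final value will be 95% x the imputed value". Values below zero are multiplied by 1.05 instead, so they fall as well. The GCCS range is given as a percentage: "The analysis will be repeated for varying penalty factors in a range between 0 and 50" (per cent). The rule fits the direction of that score, for which SAP 2.5.1 says "negative values indicate a decline from baseline while positive scores indicate improvement from baseline".

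SUVr runs the other way. Protocol 3.2 (Amyloid PET imaging) uses it to measure plaque load, and Protocol 1.1 names accumulation as the theoretical risk of neprilysin inhibition. Nothing in SAP 2.7.1.1 reverses the sign rule, says whether the factor acts on the SUVr level or on its change, or says how 1 to 1.6 relates to a percentage penalty.

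**The concern.** A tipping-point analysis is useful only if the penalty makes the imputed values worse. The sign rule in SAP 2.5.5 always lowers the value. That is correct for a z-score composite where low is bad. Carried over unchanged to SUVr, it gives penalised patients less amyloid than the missing-at-random (MAR) imputation did.

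SAP Table 2-4 lists one MNAR analysis for SUVr, and this is it. The protocol calls SUVr change a key secondary endpoint and analyses it as safety. The plan allows for about 30% information loss, deaths included. If a programmer can run the check as a bonus, a partial stress or an extreme shift, depending on the reading chosen, its result cannot support a statement that the amyloid finding is robust to MAR.

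**Working it through.** **Inputs.** From SAP 3.2: 3-year SUVr change with mean 0.03 (control) and common SD 0.03; difference to exclude 0.01; about 300 complete patients, 1:1. From SAP 3.3: 430 randomised and 30% loss. From SAP 2.5.5: multiplier (1 − p) for positive values and (1 + p) for negative values, p from 0 to 50%. From SAP 2.7.1.1: range 1 to 1.6. No SUVr level is stated in either document, so baselines of 0.7, 1.0 and 1.4 are assumed where a level is needed.

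**The plan's own figures reproduce.** With p = 5% the rule gives 0.95 and 1.05, as the SAP says. For the PET sample size, n per arm = 2 × (1.960 + 0.842)² × 0.03² / 0.01² ≈ 142. With 150 per arm, SE = 0.03 × √(2/150) = 0.00346 and power = Φ(0.01/0.00346 − 1.960) = 82%, consistent with the stated minimum of 80%. 300/0.70 = 429, against 430.

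**Rule and range together.** Putting p = 1 to 1.6 into the rule for positive values gives 1 − p = 0 to −0.6. An SUVr of zero or below is impossible, so one of the two must be dropped or reinterpreted.

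**Each workable reading.** Let X be the imputed change, X ~ N(0.03, 0.03²). Then P(X < 0) = Φ(−0.03/0.03) = Φ(−1) = 15.9%. The mean of |X| is 0.03 × 0.798 × e^(−0.5) + 0.03 × (1 − 2 × 0.159) = 0.0145 + 0.0205 = 0.035.

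| Reading | Share of imputed values moved in the favourable direction | Mean shift of imputed values |
|---|---|---|
| 2.5.5 sign rule on the change, p = 50% | 100% | −0.5 × 0.035 = −0.0175 |
| 2.5.5 sign rule on the level, p = 5% | 100% | −0.05 × (baseline + 0.03) = −0.037, −0.052, −0.072 |
| Plain multiplier 1.6 on the change | 15.9% | 0.6 × 0.03 = +0.018 (mean 0.030 to 0.048) |
| Plain multiplier 1.6 on the level | 0% | 0.6 × (baseline + 0.03) = +0.44, +0.62, +0.86 |

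A simulation of 1,000,000 changes agrees with these figures. In the third row, the negative changes fall by a further 0.0094 on average, while the other 84% rise. In the fourth row, the shift is about 15 to 29 times the SD of 0.03 under the assumed baselines.

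**Effect on the treatment difference.** The penalty is assigned by event, not by arm. If a share q_L of LCZ696 patients and q_V of valsartan patients are penalised, with mean shift δ in each arm, the difference (LCZ696 − valsartan) moves by about (q_L − q_V) × δ. Even a uniform penalty in the correct direction therefore favours LCZ696 when valsartan has more events.

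**The case against.** The best defence is that the 1 to 1.6 range replaces the percentage scale of SAP 2.5.5. A range that begins at 1 (no penalty) and rises reads most naturally as a direct multiplier. The sign rule is worded for GCCS values, and the principle stated in SAP 2.5.5 is that values may be worse than the MAR imputation. On an always-positive SUVr level, such a multiplier raises every value; on the change, the net effect is still adverse. The analysis is supportive, and Protocol 9.5.2 makes it optional.

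Much of this stands, and it rules out several stronger conclusions that a reader might infer:

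- *That the penalty certainly improves the imputed values.* It does so for all of them only if the sign rule is followed, and for a minority if the change is multiplied.
- *That the analysis cannot tip against LCZ696.* Both arms are penalised by event. If valsartan has more events, lowering SUVr pulls the valsartan mean down further and moves the difference against LCZ696.
- *That 36% of changes move the wrong way.* Φ(−0.011/0.03) gives that figure, but SAP 3.2 calls 0.011 a rate and states no period, so pairing it with a 3-year SD is not justified.
- *That a 5% step on the level overwhelms the 0.01 margin.* That compares a per-patient shift with a difference in means, and the 5% is the GCCS example; SAP 2.7.1.1 gives no step. Assuming an SUVr of 1.0 and 10% against 8% penalised, a factor of 1.05 moves the difference by 0.02 × 0.05 = 0.001, a tenth of the margin.

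A high upper end is not in itself a fault in a tipping-point search. What the defence does not remove is the text: the procedure is imported with a single exception that is not the direction, and the analysed variable named is the change, where a plain multiplier still improves the negative values.

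**Conclusion.** The point holds as a specification fault in a sensitivity analysis. The sign rule that SAP 2.7.1.1 imports runs in the favourable direction for SUVr and cannot be applied with the stated range. Depending on the reading, the share of penalised values moved in the favourable direction is 100% (sign rule), about 16% (multiplier on the change, with a net stress of +0.018 at 1.6) or none (multiplier on the level, with a very large upper end). The only MNAR check on the amyloid endpoint therefore does not reliably stress the result in the adverse direction.

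The 16% and +0.018 rest on the plan's mean of 0.03 and SD of 0.03 and on a normal distribution. The figures on the level rest on assumed baselines of 0.7 to 1.4. The main MAR analysis of SUVr, the PET sample size and the GCCS tipping point, whose direction is right, are not affected. It should be corrected before unblinding.

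**What to change.** In SAP 2.7.1.1, give SUVr its own step 2 in place of the reference to the 2.5.5 sign rule, so that the penalty always raises the imputed 3-year SUVr. Either of these would do:

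- *Additive shift.* Add a non-negative amount to the imputed value, stepped in fractions of the 0.01 margin, for example 0 to 0.06 by 0.005, and drop the 1 to 1.6 factor. This settles direction, scale and negative changes together.
- *Mirrored multiplier on the change.* Multiply positive changes by f and negative changes by (2 − f), with f from 1 to 1.6. No value is lowered; the mean shift is 0.3 × 0.035 = +0.0105 at f = 1.3 and 0.6 × 0.035 = +0.021 at f = 1.6.

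State which arm or arms are penalised, and include a run that penalises LCZ696 patients only, so that the analysis can tip against LCZ696 whatever the event imbalance. In that run the difference moves by q_L × δ: with an assumed 10% penalised, a shift of 0.06 moves it by 0.006. The grid should therefore continue until the conclusion changes or a stated limit is reached.

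The cost is a few sentences in the SAP and a changed line of code, with no added data or patient burden.
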